5.2.3. Safety Population

The safety population will consist of all subjects who are randomized and received at least one dose of investigational product (IP). Subjects will be included in the treatment group corresponding to the IP they actually received (apremilast or placebo) for the analyses and summaries using the safety population.

5.3. Baseline Definitions

For efficacy analysis and summary of baseline disease characteristics data, baseline is defined as the last value measured prior to or at the randomization date.

For safety analyses in the Placebo-controlled Phase, baseline will be relative to the first dose date following randomization at Week 0. It is the last value measured prior to or on the day of the first dose of IP.

For safety analyses in Apremilast Exposure Period, baseline will be relative to the first apremilast dose date at Week 0 for subjects initially randomized to apremilast or Week 16 for subjects initially randomized to placebo and switched to apremilast in the Extension Phase. It is the last value measured prior to or at the first apremilast dose date.

5.4. Time Points

Time points in all analyses are based on the remapped visits/study weeks using the following visit mapping algorithm, which may or may not be the same as the visits/study weeks as recorded in the database.

All visit-based data, except for those with the recorded visit being a follow-up visit, will be assigned to analysis visits based on study day (the date of assessment/collection relative to the reference date) and the defined analysis visit windows (Table 2), rather than the recorded visit. The only exception is that data with the recorded visit being a follow-up visit will be assigned to the analysis visit corresponding to the follow-up visit.

Table 2: Table for Visit Mapping

Analysis Visit	Target Day	Visit Window
Week 0 (Baseline)	1	≤1
Placebo-controlled Phase		
Week 2	15	2 – 21
Week 4	29	22 – 42
Week 8	57	43 – 70
Week 12	85	71 – 98
Week 16	113	99 – End of Phase
Apremilast Extension Phase		
Week 20	141	Start of Phase – 154
Week 24	169	155 – 196
Week 32	225	197 – End of Phase

Note: Target day and visit window are relative to the date of Visit 2/Week 0 (Day 1) randomization date. For efficacy and safety analysis, definitions for start or end dates for a phase or period are specified in Section 5.1 and Baselines are specified in Section 5.3.

Time points in the analyses or summaries of efficacy data over time include the scheduled study weeks per protocol, the end of a study phase, and the observational follow-up visit when applicable. It is possible that multiple assessment values will fall into the same visit window. The following rule may be used to select the unique value for that analysis visit:

- 1. Among all assessments in the same visit window for the analysis visit, select the value with the assessment date closest to the target day of the analysis visit;
- 2. If the relative days from 2 assessments are equally close to, but on different sides of the target day, then the latter assessment will be used for that analysis visit;

3. If multiple assessments are available on the same relative day, the duplicated values will be suppressed; otherwise, the highest value of these assessments will be used for that relative day.

For the Apremilast-exposure Period, the scheduled study weeks for placebo subjects who are treated with apremilast 30 mg BID at Week 16/Visit 7 are shown below for summaries of safety data (laboratory parameters, vital signs, etc) over time.

Table 3: Analysis Visit for Placebo Subjects Who Are Treated with Apremilast 30 mg
BID after Week 16 in the Apremilast-exposure Period

Original Visit	Analysis Visit
Week 16	Week 0 (Baseline)
Week 20	Week 4
Week 24	Week 8
Week 32	Week 16

6. STATISTICAL METHODOLOGY FOR EFFICACY

6.1. General Approaches to Efficacy Analysis

The intent-to-treat principle will be used in statistical analyses for efficacy endpoints. For the Placebo-controlled Phase (Weeks 0-16), efficacy evaluations will be conducted using the intent-to-treat (ITT) population defined as all randomized subjects. Statistical comparisons will be made between the two treatment arms (placebo or apremilast). For the Apremilast Extension Phase (Weeks 16-32), efficacy evaluations will be conducted using subjects who entered the phase from both treatment arms.

Descriptive statistics (n, mean, SD, median, Q1, Q3, min, max) will be presented for appropriate endpoints at specified time points. Specifically, for continuous variables, descriptive statistics for assessment values and change (plus percentage change when specified) from baseline will be provided. Binary variables will be summarized with frequency tabulations.

Statistical comparisons will be made between placebo arm and apremilast arm; the null hypothesis is that the effects of the two treatment arms (i.e., placebo vs. apremilast) have no difference. Statistical tests will be at the two-sided 0.05 significance level and the corresponding p-values and two-sided 95% confidence intervals (CIs) will be reported.

In the data as observed (DAO) analyses, only subjects with sufficient data at the time point under consideration will be included.

6.2. Multiplicity Adjustment

The primary and secondary efficacy endpoints will be hierarchically ranked for testing to control the overall type I error rate in claiming statistical significance at the two-sided 0.05 significance level. Specifically, for the primary efficacy endpoint (sPGA response at Week 16), if the two-sided p-value from the comparison between apremilast arm and placebo arm is below 0.05, the outcome will be considered statistically significant and apremilast will be declared effective. For any secondary endpoint, statistical significance will be claimed only if its two-sided p-value is below 0.05 and tests for the primary endpoint and all previous secondary endpoints are significant at the two-sided 0.05 level. The proposed test sequence for the primary and secondary efficacy endpoints is listed as the following:

- Proportion of subjects with an sPGA score of clear (0) or almost clear (1) with at least a 2-point reduction from baseline at Week 16
- Proportion of subjects who improved $\geq 75\%$ in BSA (BSA-75) from baseline at Week 16
- Change from baseline in affected BSA at Week 16
- Change from baseline in total PASI score at Week 16
- Proportion of subjects who achieved BSA ≤ 3% for subjects with baseline BSA > 3% at Week 16
- Proportion of subjects with ≥4-point reduction (improvement) from baseline in the whole body itch NRS score at Week 16, among subjects with baseline whole body itch NRS ≥ 4

- Proportion of subjects with ScPGA score of clear (0) or almost clear (1) with at least a 2-point reduction from baseline at Week 16, among subjects with baseline ScPGA score ≥2
- Change from baseline in DLQI total score at Week 16

6.3. Analyses of the Primary Efficacy Endpoint

The primary endpoint is the proportion of subjects who achieve sPGA response at Week 16 (defined as sPGA score of clear (0) or almost clear (1) with at least a 2-point reduction from baseline at Week 16).

The primary endpoint will be analyzed using the CMH (Cochran–Mantel–Haenszel) test adjusting for the stratification factor at randomization (mild vs. moderate sPGA). The two-sided p-values from the CMH test, the adjusted treatment difference in proportion using the weighted average of the treatment differences across the strata with the CMH weights, along with the associated two-sided 95% CIs using a normal approximation to the weighted average will be provided.

Missing values at Week 16 for this endpoint will be imputed using the multiple imputation (MI) method (SAS Institute Inc. 2011) based on similar subjects who remained in the study as the primary method. The SAS procedure MI will be used to impute missing sPGA scores at the scheduled analysis visits in the Placebo-controlled Phase (Weeks 0-16) to create M=50 complete datasets. The missing data patterns will be checked at the scheduled analysis visits, i.e., Baseline (Week 0), and Weeks 2, 4, 8, 12 and 16. If there are non-monotone missing patterns, two separate imputation procedures will be used to complete the imputation process.

In the first step, the Markov Chain Monte Carlo (MCMC) method will be used with a single chain to impute missing scores by treatment and stratification factor to create M=50 imputed datasets with monotone missing patterns. In case there are convergence issues, a simpler model will be used to impute the missing scores by treatment, with further simplification by dropping both treatment and stratification factor from the imputation model if necessary. The seed will be set to 17813721. The imputed scores will be rounded to the nearest integer. The minimum and the maximum values for imputation will be 0 and 4, which correspond to the lowest and the highest sPGA scores.

In the second step, the predictive mean matching method will be used to impute the remaining missing scores for the 50 datasets with monotone missing patterns. The imputation procedure will use the monotone statement to create one complete dataset for each of the monotone datasets from the first step, and the variables will include treatment arm, stratification factor, and sPGA scores at scheduled analysis visits from baseline to Week 16. The seed will be set to 55218163. The number of closest observations to be used in the selection will be set to 2.

After the completion of imputation, sPGA response at Week 16 will be derived based on both observed and imputed scores. The same CMH method will be used to analyze the 50 complete datasets. The SAS procedure MIANALYZE will be used to combine the results for the statistical inferences.

Sensitivity analysis will be conducted to account for missing data using the NRI (Non-responder Imputation) method and the tipping point analyses.

By NRI, subjects who have insufficient data for response determination for the time point under consideration will be considered non-responders for that time point. Insufficient data, including missing data at baseline (if the binary endpoint assesses change from baseline) or a post-baseline time point, will be determined after the handling of time points as described in Section 5.4.

For the tipping point analyses, let M1 and M2 be the total number of subjects with missing data of primary endpoint in Apremilast and Placebo. There are overall (M1+1)*(M2+1) possible ways for imputing missing data as responders or non-responders in statistical analysis, ranging from imputing all missing values as non-responders to imputing all missing values as responders in each of the two arms. For each of the (M1+1)*(M2+1) different imputation patterns, the Chisquare test will be used for testing statistical significance and the output will be plotted in a rectangle for inspection. The staircase region that separates significant and non-significant outcomes forms the tipping-point boundary.

A supplementary analysis using the PP population will also be performed.

The primary endpoint will be assessed for site effect as specified in Section 6.7.

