#### 1.3.4. Rationale for Choice of Comparator Compounds

A randomized, double-blind placebo-controlled design was chosen in order to measure the absolute treatment effect of apremilast 30 mg BID in mild to moderate plaque psoriasis. The placebo-controlled design also minimizes subject and investigator bias in evaluating the efficacy and safety of apremilast in the selected patient population (Food and Drug Administration [FDA] Guidance for Industry E10 [FDA, 2016]).

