### 8.2. Prohibited Concomitant Medications and Procedures

The following psoriasis medications cannot be administered for the duration of the study:

- Topical therapy
  - Topical therapy, including, but not limited to, topical corticosteroids, retinoids or vitamin D analog preparations, tacrolimus, pimecrolimus, or anthralin/dithranol for body lesions; coal tar, salicylic acid preparations, or medicated shampoos for scalp lesions, or as specified in Section 8.1.
- Intralesional corticosteroid injections for psoriasis lesions
- Conventional systemic therapy
  - Systemic therapy including but not limited to cyclosporine, corticosteroids, methotrexate, retinoids, mycophenolate, thioguanine, hydroxyurea, sirolimus, sulfasalazine, azathioprine, or fumaric acid esters

- Phototherapy
  - UVB or PUVA
- Biologic agents, including:
  - TNF or IL-17 blockers, anti-IL-12 or anti-IL-23 monoclonal antibodies or biosimilars for each
- Use of any investigational drug or device
- Prolonged sun exposure or any use of tanning booths or other ultraviolet light sources

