4.4. Sample Size Determination

The sample size estimation is based on the results of the Phase 3 and 4 studies with apremilast. With a total of approximately 574 subjects and a randomization ratio of 1:1, the study will randomize approximately 287 subjects to apremilast 30 mg BID and 287 subjects to placebo. This sample size will provide more than 90% power to detect a 15% difference between the two treatment groups for the primary endpoint at a two-sided significance level of 0.05. The calculation is based on a chi-square test assuming 15% response rate for placebo and adjusting for a 20% dropout rate.

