5.2.2. Per-protocol Population

The per protocol (PP) population will consist of all subjects included in the ITT population who receive at least one dose of IP, have both baseline and at least one post-treatment sPGA assessment, and have no important protocol deviations which may affect efficacy assessments in the Placebo-controlled Phase.

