11.1.2. All TEAEs

All TEAEs will be summarized by SOC and PT as well as by PT only (in descending order of subject incidence for the Placebo-controlled Phase (Weeks 0 to 16) and the Apremilast-exposure Period.

New events of all TEAEs by exposure interval (≤ 1 , > 1 to ≤ 4 , > 4 to ≤ 8 , > 8 to ≤ 12 and > 12 Weeks) will be summarized for the Placebo-controlled Phase. Each subject is counted once for either subject incidence or EAIR for each applicable specific TEAE in each exposure interval where an event started. The denominator of a subject incidence is the number of subjects with the exposure time reaching the lower bound of the particular exposure interval, and the denominator of an EAIR is the sum of the exposure time during the exposure interval (up to the start date [inclusive] of the first occurrence of the specific event for each subject reporting the event in the interval) among the same number of subjects as in the denominator of the corresponding subject incidence.

In addition, new events of all TEAEs by exposure interval (≤ 1 , > 1 to ≤ 8 , > 8 to ≤ 16 , > 16 to ≤ 24 , > 24 to ≤ 32 , > 32 Weeks) will be summarized for the Apremilast-exposure Period.

All TEAEs will be summarized by age category ($< 65, \ge 65$ years), sex, race (white vs. non-white), baseline sPGA categories (sPGA =2; sPGA =3) and, if deemed necessary, by prior/concomitant psoriasis medication usage or baseline disease characteristics.

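### A Week 16 response scored after starting a prohibited psoriasis therapy counts as a response; only the per-protocol analysis might react, and it would drop the subject rather than count a failure

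*SAP*

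**What the plan says.** SAP 6.3 defines response by the sPGA score only: 0 or 1 at Week 16, with a drop of two or more points. It derives response from observed scores plus imputed ones. Multiple imputation fills missing scores. Under NRI, "subjects who have insufficient data for response determination for the time point under consideration will be considered non-responders for that time point", and the SAP explains insufficient data in terms of missing assessments after visit windowing. The tipping-point analysis varies only the subjects with a missing primary endpoint.

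SAP 6.4.1 applies a similar imputation and the same NRI rule to the binary secondary endpoints. Protocol 9.6.1.2 also lists LOCF for them, which again acts only on missing values.

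On other treatment, Protocol 8.2 states: "The following psoriasis medications cannot be administered for the duration of the study". Neither document links such use to response status. Protocol 11.1 lists protocol deviation and lack of efficacy as sufficient reasons to stop study drug, so a user may still be in the study at Week 16.

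The per-protocol population keeps subjects who, among other conditions, "have no important protocol deviations which may affect efficacy assessments in the Placebo-controlled Phase" (SAP 5.2.2). SAP 10 leaves the classing of deviations as important to a standard procedure of the sponsor or CRO and does not name prohibited medication. SAP 6.3 specifies the per-protocol analysis for the primary endpoint; SAP 6.4 does not mention one for the secondary endpoints.

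**The concern.** Protocol 1.3.4 says the placebo-controlled design was chosen "to measure the absolute treatment effect of apremilast 30 mg BID". A clear or almost clear score reached after starting, say, a topical corticosteroid is not evidence about apremilast, nor about what placebo alone achieves. Yet it enters the response count unchanged, and the analyses labelled as sensitivity analyses leave it unchanged too.

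Subjects enter off topical therapy and are meant to stay off it, so use of a prohibited therapy is most plausible where study treatment is failing, which points to more use on placebo. That would raise the placebo rate and shrink the difference. More use on apremilast would inflate it. The itch, scalp and BSA ≤ 3% endpoints are analysed in baseline-defined subsets, where a few such subjects can weigh more. A lost step in the fixed testing sequence also blocks every later one.

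**Working it through.** **1. Trace one subject.** A subject starts a Section 8.2 therapy before Week 16, stays in the study, and has an observed Week 16 score that meets the response definition.

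- Primary analysis: the score is observed, so nothing is imputed. Responder.
- NRI: data are sufficient. Responder.
- Tipping point: not among the subjects with missing data. Responder in every cell of the grid.
- Binary secondary endpoints: same logic wherever the Week 16 value qualifies.
- Per-protocol (primary endpoint): excluded if the use is classed as an important deviation affecting efficacy; otherwise a responder. In no case a failure.

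**2. Reproduce the plan's own figure.** SAP 4.4 says "This sample size will provide more than 90% power to detect a 15% difference between the two treatment groups", "assuming 15% response rate for placebo and adjusting for a 20% dropout rate", with 287 subjects per arm and a two-sided 0.05 chi-square test.

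- Evaluable per arm: n = 287 × 0.8 = 229.6. Rates 0.15 and 0.30, pooled rate 0.225.
- SE under the null = √(2 × 0.225 × 0.775 / 229.6) = 0.0390.
- SE under the alternative = √((0.15 × 0.85 + 0.30 × 0.70) / 229.6) = 0.0383.
- Power = Φ[(0.15 − 1.96 × 0.0390) / 0.0383] = Φ(1.92) = 97.3%.

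The stated figure holds and is not in dispute.

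**3. Size of the shift.** The documents give no rate of prohibited use and no response rate after it, so both are assumptions. Users are taken to be subjects who would otherwise not respond and who have an observed Week 16 score. The 50% upper value is a loose reading of Protocol 1.1, where about half of subjects on a combination topical did not reach a meaningful reduction at 4 weeks, so about half did. The 20% lower value is assumed.

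Observed rate = planned rate + (share using) × (response once treated).
Difference = 15 − (placebo use − apremilast use) × (response once treated), in points.

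| Use, placebo / apremilast | Response once treated | Rates, placebo / apremilast | Difference (points) | Power at 229.6 per arm |
|---|---|---|---|---|
| 3% / 1% | 20% | 15.6% / 30.2% | 14.6 | 96.3% |
| 3% / 1% | 50% | 16.5% / 30.5% | 14.0 | 94.5% |
| 5% / 2% | 20% | 16.0% / 30.4% | 14.4 | 95.7% |
| 5% / 2% | 50% | 17.5% / 31.0% | 13.5 | 92.4% |
| 10% / 3% | 20% | 17.0% / 30.6% | 13.6 | 93.1% |
| 10% / 3% | 50% | 20.0% / 31.5% | 11.5 | 80.7% |
| 2% / 5% (reverse) | 20% | 15.4% / 31.0% | 15.6 | 97.9% |
| 2% / 5% (reverse) | 50% | 16.0% / 32.5% | 16.5 | 98.6% |

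Under these assumptions, scoring the users as failures returns 15% against 30%, a difference of 15 points.

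**The case against.** The strongest reply is that the expected pattern works against the drug. If use is mostly on placebo, the difference shrinks, and the other therapy cannot be what produces a significant result. That stands. A reader might infer that the plan is tilted towards apremilast, or that a positive result could not be credited to it. The documents do not support either: inflation needs heavier use on apremilast, and nothing in them suggests that.

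The inputs are also soft. The 50% value comes from a different endpoint over 4 weeks. Here a subject entering at sPGA 2 must clear completely to respond, and all subjects were inadequately controlled with, or intolerant of, at least one topical. The true figure may well be lower, which is why a range is shown. Among the placebo-heavy rows, only 10%/3% at 50% response takes power below the stated 90%.

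Existing safeguards count for something. The per-protocol analysis can hint at whether these subjects matter. Deviations are listed before Week 16 unblinding and tabulated by arm (SAP 10), and concomitant medications are summarized by arm (SAP 8.5). A user who leaves with no score in the Week 16 window is already an NRI non-responder. But exclusion after randomization is not the same as counting a failure, and a medication table does not change a response rate.

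A reader might also take SAP 11.1.2 as showing that the authors expect on-study psoriasis medication. It provides for adverse event summaries "by prior/concomitant psoriasis medication usage or baseline disease characteristics", but only if deemed necessary, and it covers prior use as well. It shows no such expectation.

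Finally, using observed scores regardless of other medication fits the intent-to-treat principle of SAP 6.1. That is a good reason to keep the primary analysis. It is not a reason to have no analysis that answers the other question.

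**Conclusion.** The gap is real but modest. For an observed Week 16 score the stated derivation allows only one outcome, although no sentence says outright that a response on prohibited therapy counts. It would go too far to say that no planned analysis reacts: the per-protocol analysis of the primary endpoint may, by exclusion.

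Under the assumed placebo-heavy use, the 15-point difference becomes about 14.6 to 11.5 points; the reverse pattern at 50% response gives 16.5. These figures rest on assumed use and response rates and on users otherwise being non-responders. The likelier direction is conservative, so this does not undermine the primary analysis. It is a cheap improvement that would let the trial show how far its response rates depend on other psoriasis therapy.

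**What to change.** Keep the primary, NRI and tipping-point analyses as they are. Add to SAP 6.3, and by reference to 6.4.1, a separate supplementary analysis: a subject who starts any psoriasis therapy listed in Protocol 8.2 on or before the Week 16 assessment is a non-responder, even if a Week 16 score exists, with missing data otherwise handled as in the primary analysis. The rule should not be folded into NRI. NRI is there to test sensitivity to missing data, and a medication rule would change two things at once.

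Identify these subjects in the blinded deviation review that SAP 10 already places before the Week 16 unblinding, and tabulate them by arm afterwards. Protocol 8.1 already requires medication dates and indications to be recorded.

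The cost is one extra analysis, in which response rates may be slightly lower. It covers the binary endpoints only; the MMRM analyses of change in BSA, PASI and DLQI also use observed values, and a non-responder rule does not reach them.

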#### 9.6.1.1. Primary Efficacy Endpoint

The primary endpoint is the proportions of subjects who achieving sPGA response at Week 16 (defined as sPGA score of clear [0] or almost clear [1] and with at least a 2-point reduction from baseline at Week 16). It will be analyzed using the ITT population. A sensitivity analysis will be performed using the PP population.

The primary endpoint will be analyzed using the Cochran–Mantel–Haenszel (CMH) test adjusting for the stratification factor at randomization. The two-sided p-values from the CMH test, the adjusted treatment difference in proportion using the weighted average of the treatment differences across the strata with the CMH weights, along with the associated two-sided 95% CIs using a normal approximation to the weighted average will be provided.

Missing values at Week 16 will be imputed using the multiple imputation (MI) method (SAS Institute Inc., 2011) based on similar subjects who remained in the study as the primary method. Sensitivity analysis will be conducted to account for missing data using the non-responder imputation (NRI) method and the tipping point analysis. Details of the NRI method and the tipping point analysis will be provided in the Statistical Analysis Plan (SAP).

For the multiple imputation method, the SAS procedure MI will be used to impute missing sPGA scores at the scheduled analysis visits in the Placebo-controlled Phase (Weeks 0 to 16) to create M=50 complete data sets. The missing data patterns will be checked at the scheduled analysis visits, ie, Baseline (Week 0), and Weeks 2, 4, 8, 12 and 16. If there are non-monotone missing patterns, two steps will be used to complete the imputation process.

In the first step, the Markov Chain Monte Carlo (MCMC) method will be used with a single chain to impute missing scores by treatment and stratification factor to create M=50 imputed data sets with monotone missing patterns. In case there are convergence issues, a simple model will be used to impute the missing scores by treatment, with further simplification by dropping both

treatment and stratification factor in imputation model if necessary. The seed will be set to 17813721. The imputed scores will be rounded to the nearest integer. The minimum and the maximum values for imputation will be 0 and 4, which correspond to the lowest and the highest sPGA scores.

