6.4.1. Binary Variables

The binary variables for secondary endpoints include the following:

- Proportion of subjects who improved ≥ 75% in BSA (BSA-75) from baseline at Week
 16
- Proportion of subjects who achieved BSA ≤ 3% for subjects with baseline BSA > 3% at Week 16
- Proportion of subjects with ≥4-point reduction (improvement) from baseline in the whole body itch NRS score at Week 16, among subjects with baseline whole body itch NRS ≥ 4
- Proportion of subjects with ScPGA score of clear (0) or almost clear (1) with at least a 2-point reduction from baseline at Week 16, among subjects with baseline ScPGA score > 2

For these binary endpoints, the treatment difference between apremilast arm and placebo arm will be compared using CMH test adjusting for the stratification factor at randomization. The two-sided p-values from the CMH test, the adjusted treatment difference in proportion using the weighted average of the treatment differences across the strata with the CMH weights, along with the associated two-sided 95% CIs using a normal approximation to the weighted average will be provided.

Missing values will be imputed using the similar MI method as the primary endpoint, with sensitivity analysis using the NRI method as described in section 6.3.

Further, analyses of the following secondary endpoints will be performed for the subjects with baseline sPGA = 2 (mild psoriasis) and sPGA = 3 (moderate psoriasis):

- Proportion of subjects who improved ≥ 75% in BSA (BSA-75) from baseline at Week
 16
- Proportion of subjects who achieved BSA ≤ 3% for subjects with baseline BSA > 3% at Week 16
- Proportion of subjects who achieved BSA ≤ 1% for subjects with baseline BSA > 1% at Week 16

The treatment difference between apremilast arm and placebo arm will be compared using Chi-squared test. The two-sided p-values from the Chi-squared test, the treatment difference in proportion, along with the associated two-sided 95% CIs will be provided.

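### Should the tipping-point grid use the stratified CMH test of the primary analysis instead of a plain chi-square?

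*SAP*

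**What the plan says.** The primary analysis in SAP 6.3 is a CMH "test adjusting for the stratification factor at randomization (mild vs. moderate sPGA"). For the multiple imputation, "The same CMH method will be used to analyze the 50 complete datasets", with the results then pooled.

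The same section lists two sensitivity analyses for missing data: NRI and the tipping point. For the tipping point it counts missing subjects in each arm, M1 on apremilast and M2 on placebo. It forms every combination of responder counts among them and states: "For each of the (M1+1)*(M2+1) different imputation patterns, the Chisquare test will be used for testing statistical significance". The outcomes are plotted for inspection. Neither stratum nor any rule for placing imputed responders in strata is mentioned, so the test can only be a chi-square on arm totals. The SAP does not name the test used for NRI.

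The protocol does not settle the matter. Section 9.6.1.1 says: "Details of the NRI method and the tipping point analysis will be provided in the Statistical Analysis Plan (SAP"). Among its efficacy analyses, the SAP names a chi-squared test in one other place, section 6.4.1, for analyses within a single baseline sPGA category: "The treatment difference between apremilast arm and placebo arm will be compared using Chi-squared test". There is no stratum to adjust for there.

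**The concern.** A tipping-point display shows how far the missing-data assumption must move before the primary result is lost. Its boundary should then refer to the primary test. Here it mixes a change of assumption with a change of test.

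The mismatch is most visible in the corner where all missing subjects are non-responders. That cell is the same dataset as NRI. If NRI uses the CMH, as the section implies, two sensitivity outputs would carry different p-values for identical data.

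Stratification could also matter for this endpoint. A subject who starts at sPGA 2 must reach 0 to respond, while one who starts at 3 may reach 0 or 1, so response rates may well differ by stratum. If the two tests diverged much, a reader could be misled about how robust the primary result is.

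**Working it through.** **The plan's own figure.** SAP 4.4 uses "a two-sided significance level of 0.05" and says: "This sample size will provide more than 90% power to detect a 15% difference between the two treatment groups for the primary endpoint", "assuming 15% response rate for placebo and adjusting for a 20% dropout rate". The sizing is itself based on an unstratified chi-square. With 287 × 0.8 ≈ 229 completers per arm and mean rate 0.225:

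z = [0.15·√229 − 1.96·√(2·0.225·0.775)] / √(0.15·0.85 + 0.30·0.70) = (2.270 − 1.157)/0.581 = 1.915, which is 97.2% power. The stated figure is reproduced.

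**Inputs for the grid.** 287 per arm, with strata of about 30% and 70% (SAP 4.3), taken as 86 mild and 201 moderate. Missing 20%: 17 + 40 = 57 per arm, so 58 × 58 = 3364 cells. Stratum response rates are assumed. No continuity correction; critical value 3.84.

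**The two statistics in the all-non-responder cell.** Take 69 apremilast and 34 placebo responders (30% and 15% of the observed subjects).

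- Chi-square = 574·(69·253 − 34·218)² / (287·287·103·471) = 14.49.
- CMH = [Σ(aₖ − Eₖ)]² / ΣVₖ. With equal arms in each stratum of total size Nₖ with mₖ responders, Eₖ = mₖ/2, the sum in the numerator is (69 − 34)/2 = 17.5 however responders are split, and Vₖ = 0.25·mₖ(Nₖ − mₖ)/(Nₖ − 1).
- Equal strata (21 + 48 v 10 + 24): V = 6.390 + 14.813 = 21.203, so CMH = 306.25/21.203 = 14.44.
- Mild lower (10 + 59 v 3 + 31): V = 3.022 + 17.506 = 20.528, so CMH = 14.92.
- Mild much lower (3 + 66 v 1 + 33): V = 0.982 + 18.701 = 19.684, so CMH = 15.56.

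The arm totals are the same, with one chi-square and three CMH values. This is the central point: M1 and M2 do not determine a CMH.

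**Full grid, 57 missing per arm.** Imputed responders are split between strata in proportion to the missing counts. The last column counts cells whose CMH verdict changes over all possible splits.

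| Assumed rates, placebo/apremilast %, mild; moderate | Chi-square / CMH at (0,0) | Cells that disagree | Largest row shift | Split-dependent cells |
|---|---|---|---|---|
| 15/30; 15/30 | 14.49 / 14.44 | 2 (0.06%), chi-square only | 1 | 10 |
| 5/15; 19.3/36.4 | 14.49 / 14.92 | 10 (0.30%), CMH only | 1 | 35 |
| 2/5; 20.6/40.7 | 14.49 / 15.56 | 28 (0.83%), CMH only | 1 | 49 |
| 5/12; 19.3/30 | 6.38 / 6.54 | 10 (0.30%), CMH only | 1 | 36 |
| 20/35; 13/28 | 13.57 / 13.59 | 0 | 0 | 16 |
| 25/45; 11/24 | 14.28 / 14.61 | 9 (0.27%), CMH only | 1 | 31 |
| 30/50; 9/21 | 12.88 / 13.61 | 21 (0.62%), CMH only | 1 | 46 |
| 40/60; 4/17 | 13.78 / 16.07 | 50 (1.49%), CMH only | 2 | 70 |

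Row shift is the change in the number of placebo imputed responders that the result can absorb, for a given apremilast count. Rounding the assumed counts differently moves the disagreeing cells by a few.

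With 10% missing (29 per arm, 900 cells), the first two rows give 1 and 2 disagreeing cells and a shift of at most one subject.

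**Direction.** Where stratum rates differ enough to matter, whichever stratum responds more, the disagreeing cells are significant by CMH only, so the chi-square is slightly conservative. With equal rates, a couple of cells go the other way.

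**The case for a change.** The best case for a change is consistency. In the efficacy analyses the SAP otherwise uses chi-square only where there is no stratum, and the switch is unexplained. A CMH grid costs a modified loop, and a proportional split would make the corner cell match NRI. If the data fell near the line, that cell and NRI could land on opposite sides of 0.05.

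The textual point stands: the tests differ and the SAP does not say why. The rest is weak.

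- A CMH grid needs an allocation rule that the plan does not have and the data cannot supply. In every case above, more cells depend on that rule than change by switching test: 10 against 2, 35 against 10, 49 against 28, 70 against 50. One reproducible staircase would become a band.
- Even then the grid would not match the primary result, because each cell is a single completed dataset while the primary result pools 50 imputations.
- Opposite verdicts in the corner cell need a statistic close to 3.84. Outside the extreme last row, the CMH there lies between 0.3% below and about 7% above the chi-square. A result that close to the line would be read as fragile under either test.
- That the corner differs from NRI presumes NRI uses CMH. This is the likelier reading, but the gap at planning rates is then 14.49 against 14.44 to 15.56.

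**Conclusion.** No change to the plan follows. The chi-square is the test that the arm-total grid determines, and the plan already uses it as a stand-in for the CMH in the sample size calculation. Using CMH instead would trade a small mismatch for a larger arbitrary element, with no gain in what the display tells the reader.

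The size, at 20% missing and under assumed stratum rates: disagreement in at most 0.8% of cells and a boundary shift of at most one placebo subject. In the extreme case of mild subjects responding far more often, this rises to 1.5% and two subjects. The chi-square is mostly the more cautious of the two. The grid has no decision rule and lies outside the testing sequence in SAP 6.2, so the primary test, type I error and power are untouched.

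That the NRI test is unnamed is a gap the analyst will fill with the section's CMH. A table footnote that the grid is unstratified would tell the reader why its corner cell differs slightly from NRI, and that needs no amendment.

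The conclusion rests on stratum rates that the documents do not give, on strata near 30% and 70%, and on equal arms. The rates tried cover both directions of stratum difference.
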